#### 12.3 Informed Consent Procedure

The investigator is responsible for giving the patients full and adequate verbal and written information about the nature, purpose, possible risk and benefit of the study. They will be informed as to the strict confidentiality of their patient data, but that their medical records may be reviewed for trial purposes by authorized individuals other than their treating physician.

It will be emphasized that the participation is voluntary and that the patient is allowed to refuse further participation in the protocol whenever she/he wants. This will not prejudice the patient's subsequent care. Documented informed consent will be obtained for all patients included in the study before they are registered in the study.

A copy of the patient information and consent will be given to the patients. The signed and dated patient consent forms will be filed by the investigator. A professional interpreter will be used if required.

#### 12.4 Subject Identification

The investigator is responsible for keeping a list of all patients (who have received study treatment or undergone any study specific procedure) including patient's date of birth and personal number, full names and last known addresses.

The patients will be identified in the eCRFs by patient number, initials and date of birth.

### 13 Trial sponsorship and financing

The study is sponsored by Norsk Forskiningsråd with project number 288579. ChromaDex (USA), the company producing the NR supplies NR and placebo for free.

#### 14 Trial insurance

Since True Niagen is classified as a nutritional supply and not a drug, the Produktansvarslov does not apply. Participants may however apply for compensation to the Norwegian Health Service Litigation Authority (Norsk Pasienterstatning) should they suffer injury or develop adverse reactions to NR.

### 15 Publication policy

Upon study completion and finalization of the study report, the results of this study will be submitted for publication in an international peer reviewed journal.

All personnel who have contributed significantly with the planning and performance of the study (Vancouver convention 1988) may be included in the list of authors.

#### 17 APPENDICES

A. Forms and questionnaires

- B. Safety committee charter
- C. Statistical analysis plan
- D. Consent form
- E. Amendment 1

1.1 Background and rationale

Below follows a short summary from "Background and rationale" from study Protocol (B3Short study: shorter recovery time after critical illness. Protocol ID number 2017/1334C. Version number 1.46 dated June 12, 2023, by Oslo University Hospital, Department of Microbiology).

Please see protocol for list of references.

Background

Patients recovering from acute illness often experience prolonged recovery times, influenced by factors such as age, illness duration, and severity. Impaired mitochondrial energy production due to inflammation-induced depletion of nicotinamide adenine dinucleotide (NAD+) may contribute to prolonged recovery phase.

Therapeutic Information

Nicotinamide riboside (NR) is an orally available, safe NAD+ precursor that has been shown to restore NAD+ levels in humans and prolong life in old mice.

Rationale for the Study

Recovery from acute illness is associated with increased risks and delayed or incomplete recovery is common. No "recovery-improvement drug" currently exists. The study aims to administer NR or placebo for 90 days to patients in the recovery phase.

1.2 Trial Objectives

Primary Objective

The primary objective of this study is to assess the efficacy of dietary supplement NR on shortening recovery time after critical illness.

Secondary Objectives

The secondary objectives of this study are:

- To assess the effect of NR on mortality
- To assess NR adverse events
- Other secondary objectives are described in the protocol but will not feature in the main publication

2 Trial Methods

2.1 Trial Design

The B3SHORT study is designed as a double-blinded, randomized, three-phase, superiority study where three different doses of NR will be compared to placebo for its efficacy of shortening hospital stays after acute illness. The doses, allocation ratios, and sample size in the three phases are given in Table 1.

Table 1: Doses, allocation ratios, and sample size for the B3SHORT study

	Dose of NR	Dose label	Allocation ratio	Number of patients in the NR group	Number of patients in the placebo group
Phase #1	250 mg/day	Low dose	5:3	10	6
Phase #2	500 mg/day	Medium dose	5:3	10	6
Phase #3	1 g/day	Normal dose	10:3	20	6
Total				40	18

2.2 Randomization

Eligible patients are allocated in a 5:3 (phases 1 and 2) or 10:3 (phase 3) ratio between NR and placebo, using a computer randomization procedure. The randomization is blocked within each phase. Details of block size and allocation sequence generation is provided in a separate document unavailable to those who enroll patients or assign treatment.

Details of the randomization including the final random allocation list are held securely and unavailable to unauthorized trial personnel.

2.3 Sample size

Assuming the time of hospitalization after randomization follows a Weibull distribution with a scale parameter λ = 18 and shape parameter κ =2.2 (corresponding to a median of 15 and an IQR of 10 – 21), we need to include 58 patients: 18 in the placebo group, 10 in the 250 mg/day group, 10 in the 500 mg/day group, and 20 in the 1 g/day group) in order to reach approximately 80% power to show a significant dose-response in this study with a maximal reduction in time of hospitalization of 33%. This calculation is based on optimal designs in dose-finding studies according to the MCPMod methodology with three alternative dose-response curves: linear, e-max and exponential (Pinheiro et al., 2014).

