### 10 Statistical methods and data analysis

#### 10.1 Determination of Sample Size

A total of 58 patients will be recruited The number of dropouts is unknown, but the power calculation assumes only 58 randomized patients.

Assuming the time of hospitalization after randomization follows a Weibull distribution with a scale parameter  $\lambda$  = 18 and shape parameter  $\kappa$ =2.2 (corresponding to a median of 15 and an IQR of 10 – 21), we need to include 58 patients (18 in the placebo group, 10 in the 250 mg and 500 mg group and 20 in the 1000 mg group) in order to reach approximately 80% power to show a significant dose-response in this study with a maximal reduction in time of hospitalization of 33%. This calculation is based on optimal designs in dose-finding studies according to the MCPMod methodology with three alternative dose-response curves (linear, e-max and exponential)(Pinheiro, Bornkamp et al. 2014).

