2.4 Statistical Framework

The statistical framework will be based on the context of dose-finding, for which there are two main approaches: "regression" and "contrast" (Senn, 2007). In the regression approach, the actual doses used in the trial are viewed as samples from a dose continuum, and the purpose is to estimate the dose response curve. In the contrast approach, interest is on one or (more likely) several contrasts between the doses used in the trial. The former is the most explorative and may be sensitive to modeling choices, small number of doses, and over-fitting, especially for small sample sizes (such as in this trial). The latter is well suited for determining the *minimum effective dose*, in which we compare the different doses to placebo.

Specification of the Primary Objective

The primary objective of this study will be to establish the minimum effective dose of NR on shortening recovery time after critical illness. The primary outcome is length of hospital stay in days (see Section 5.1 for details).

There is only one identified primary analysis in this trial. All other efficacy analyses will be regarded as supportive or exploratory.

Hypothesis Setup

Let μ_1 , μ_2 , μ_3 , and μ_4 denote the mean lengths of hospital stay for placebo, low dose (250 mg/day), medium dose (500 mg/day), and normal dose (1 g/day), respectively.

The statistical scheme to account for multiple testing is based on the *closed multiple test procedure* of Marcus et al. (1976). Under the monotonicity assumption, we define a set of elementary null hypotheses (the many-one comparison) with a preassigned order of performing the tests (Williams, 1971):

Step 1: Test the null hypothesis H_0 : $\mu_1 = \mu_4$ Step 2: Test the null hypothesis H_0 : $\mu_1 = \mu_3$ Step 3: Test the null hypothesis H_0 : $\mu_1 = \mu_2$

The test in Step 1 is carried out with a nominal significance level of α = 0.05. If the test is rejected, the test in Step 2 can be carried out, also with α = 0.05. If the test in Step 2 is rejected, the test in Step 3 can be carried out (with α = 0.05). The tests in steps 2 and 3 are only performed if the preceding null hypothesis is rejected, which – together with the monotonicity assumption – ensures that the significance level is preserved for the entire procedure (Williams, 1971; Bauer, 1991). All tests will be performed two-sided.

Decision Rule

The testing scheme above can result in four situations:

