- 1. The null hypothesis in Step 1 is not rejected. Decision: No effect of NR for the doses in the study.
- 2. The null hypothesis in Step 2 is not rejected. Decision: The normal dose is the minimum effective dose.
- 3. The null hypothesis in Step 3 is not rejected. Decision: The medium dose is the minimum effective dose.
- 4. The null hypothesis in Step 3 is rejected. Decision: The low dose is the minimum effective dose.

Assumption

The dose response is assumed to be monotone, i.e., the effect of low dose is less than or equal to the effect of medium dose, which is less than or equal to the effect of normal dose. Or, consequently, that the mean length of hospital stay decreases monotonous from placebo (μ_1) to normal dose (μ_4):

 $\mu_1 \ge \mu_2 \ge \mu_3 \ge \mu_4$.

Adaptation to Estimation

Hypothesis testing will only be performed for the primary outcome. For all secondary outcomes, estimation of treatment effect with 95% (two-sided) confidence intervals will be carried out instead of hypothesis testing in each of the three steps described above. The overall statistical approach will be the same; however, the criterion for performing steps 2 and 3 is that the 95% confidence interval from the preceding step does not contain the null effect value.

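### The 80% power belongs to an MCPMod test that is not planned; the gated primary analysis has about 77% at Step 1 and far less at the steps that set the minimum effective dose

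*SAP*

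**What the plan says.** SAP 2.3 sets the sample at 58 (18 placebo, 10, 10 and 20 on the three doses) "in order to reach approximately 80% power to show a significant dose-response in this study". Protocol 10.1 gives the same calculation and its source: "This calculation is based on optimal designs in dose-finding studies according to the MCPMod methodology", with linear, e-max and exponential candidate curves. The parameters of the last two curves are not given.

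SAP 2.4 then takes another route. It notes that curve modelling may be fragile, "especially for small sample sizes (such as in this trial"), and adopts contrasts with placebo. It restates the aim: "The primary objective of this study will be to establish the minimum effective dose of NR on shortening recovery time after critical illness". It adds: "There is only one identified primary analysis in this trial". That analysis tests normal dose, then medium, then low against placebo, each two-sided at 0.05, and "The tests in steps 2 and 3 are only performed if the preceding null hypothesis is rejected". Under SAP 6 and 6.1 each step is a two-group Weibull model using only that dose group and placebo.

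The decision rule in SAP 2.4 includes "The null hypothesis in Step 1 is not rejected. Decision: No effect of NR for the doses in the study" and "The null hypothesis in Step 2 is not rejected. Decision: The normal dose is the minimum effective dose".

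The planned sensitivity analyses are the per-protocol set, a Cox model, and a Cox model with imputation for deaths. A pooled comparison of all NR doses with placebo is exploratory. No MCPMod or other dose-response test is listed, and no power is given for Step 1, 2 or 3.

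**The concern.** The only power figure in the plan describes a test that will not be run. MCPMod borrows strength across all four groups through a contrast. The stepwise tests use 38, 28 and 28 patients separately, and the later ones are reached only through the earlier ones. A reader looking for the power of the primary analysis finds 80% and nothing else.

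Two conclusions are exposed. SAP 1.2 asks whether NR shortens recovery, and Step 1 answers that. SAP 2.4 asks for the minimum effective dose, and Steps 2 and 3 answer that. If those steps are weak, the word *minimum* rests on a failure to reject in a small comparison. The first outcome of the decision rule goes further: it equates a non-significant Step 1 with absence of effect, and extends this to two doses that would not have been tested at all.

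**Working it through.** **Inputs.** From SAP 2.3: hospital stay Weibull with scale 18 and shape 2.2; maximal reduction 33%; groups of 18, 10, 10 and 20. From SAP 2.4: two-sided 0.05 at each step, with gating. Assumed: no censoring, a Wald test, e-max ED50 of 100–500 mg and exponential delta of 250–1000 mg.

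**The plan's own figures.** The Weibull gives a median of 15.2 and an IQR of 10.2–20.9, matching the stated 15 and 10–21. An MCPMod contrast test on log time (variance (1/2.2)²/n per arm, two-sided 0.05, assumed ED50 100–500 mg and delta 250–500 mg) has 77–83% power by curve and about 79–80% averaged over the three. The stated 80% is therefore reproduced for the test it describes.

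**Step 1 (20 v 18).**
- Planned log HR = 2.2 × ln(1/0.67) = 0.881, so HR = 2.41 for discharge.
- SE = √(1/20 + 1/18) = 0.325.
- Power = Φ(0.881/0.325 − 1.96) = 77.4%. For 80%, 41 events are needed; 38 are available.
- Significance needs an observed HR of at least exp(1.96 × 0.325) = 1.89, a 25.1% reduction.
- The 95% CI contains 2.41 when the observed HR exceeds 2.41/1.89 = 1.28, a 10.5% reduction. Observed HRs between about 1.28 and 1.89 are thus non-significant yet compatible with the planned effect.

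**Steps 2 and 3 (10 v 18 each).**
- SE = √(1/10 + 1/18) = 0.394. Significance needs an observed HR of at least 2.17, a 29.6% reduction.
- Without gating, power at a true 33% reduction is 61%; 80% power would need a 39.5% reduction.

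**Gated power.** Simulation with shared placebo, 40,000 trials per scenario, Monte Carlo error about 0.5 points. Step 2 counts only if Step 1 rejects, and Step 3 only if both reject. The pooled column is the exploratory 40 v 18 comparison, assuming the same Weibull model.

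| Dose-response | Reduction at 250 / 500 / 1000 mg (%) | Steps 1 / 2 / 3 (%) | Pooled (%) |
|---|---|---|---|
| Linear | 8.2 / 16.5 / 33 | 76.6 / 18.4 / 3.8 | 44.7 |
| E-max, ED50 100 | 25.9 / 30.3 / 33 | 76.4 / 46.6 / 26.3 | 78.6 |
| E-max, ED50 250 | 20.6 / 27.5 / 33 | 76.2 / 40.5 / 16.8 | 70.8 |
| E-max, ED50 500 | 16.5 / 24.8 / 33 | 76.1 / 33.9 / 11.1 | 63.7 |
| Exponential, delta 250 | 1.1 / 3.9 / 33 | 76.4 / 6.4 / 0.8 | 24.5 |
| Exponential, delta 500 | 3.4 / 8.9 / 33 | 76.6 / 9.6 / 1.4 | 31.0 |
| Exponential, delta 1000 | 5.5 / 12.5 / 33 | 76.2 / 13.0 / 2.2 | 36.9 |
| 33% at every dose (not a plan curve) | 33 / 33 / 33 | 76.4 / 53.3 / 40.6 | 85.4 |

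The linear row needs no assumed curve parameter.

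**What the decision rule would state.** With 33% at every dose, the rule reports no effect in 23.6% of trials and names the normal dose in 23.2%, the medium in 12.7% and the low in 40.6%. It therefore names too high a dose in 23.2 + 12.7 = 35.9%. In every scenario, 88–89% of Step 1 non-rejections have a 95% CI containing 2.41; the median upper limit is 3.16. Among those trials the pooled comparison is significant in 4% (linear), 15–33% (e-max), 1–3% (exponential) and 47% (33% at every dose).

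**Robustness.** With an assumed 10% of patients censored by death, the linear row becomes 73.2 / 17.0 / 3.3%. Under the null the Wald test rejects 6.3% at Step 1 and 6.8% for 10 v 18, so the powers above are, if anything, slightly favourable.

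**The case against.** The strongest reply is that no stated figure is wrong. The SAP names MCPMod as the source of the 80%, and its next section explains why contrasts are used instead. For the test that decides whether any effect is claimed, the shortfall is only 3–4 points against a figure given as approximate. All of this stands, but naming the source of another test's power does not supply the power of the primary one.

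The miss rate of about 1 in 4 is mostly ordinary type II error, since a test with exactly 80% power misses 1 in 5. Likewise the 89% follows almost directly from the power: (0.226 − 0.025)/0.226 = 89%, and an 80%-power test would give 87.5%. Both points are fair. They show that the fault lies in the decision wording, which would be unsound at 80% too.

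The 18% and 4% under the linear curve owe more to small assumed effects at the lower doses than to gating: without the gate, Step 2 has only about 20%. That is correct, but the linear curve is the plan's own, and even the full effect at every dose leaves Step 3 at 41%.

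Finally, the sample is fixed, and SAP 6.1 already plans means, standard deviations, individual values and Kaplan-Meier curves for every dose, alongside the pooled comparison. These help, but none gives a hazard ratio with interval for a dose whose step was not reached, and none alters the pre-specified conclusion.

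**Conclusion.** The concern holds and should be fixed. The 80% is sound for MCPMod but does not describe the primary analysis. Step 1 has about 76–77% power. With gating, Steps 2 and 3 have about 18% and 4% (linear), 34–47% and 11–26% (e-max), 6–13% and 1–2% (exponential), and 53% and 41% if every dose gave 33%. The e-max and exponential ranges rest on assumed parameters, but Step 2 stays below 50% throughout them.

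The first outcome of the decision rule is wrong as written, because non-rejection does not establish absence of effect. In the second and third outcomes the named dose has itself beaten placebo; only the word *minimum* is unsupported. All figures assume the plan's Weibull, a 33% reduction at the normal dose and no deaths or dropouts.

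**What to change.** 1. **SAP 2.3.** Keep the present text as the record of how 58 was chosen, and add: *The 80% refers to an MCPMod dose-response test, which is not among the planned analyses. For the stepwise procedure in Section 2.4, under the same Weibull assumption, a 33% maximal reduction and no censoring, power is about 77% at Step 1. With gating and a linear dose-response it is about 18% at Step 2 and 4% at Step 3.* So that the linear case does not stand alone, the sponsor should add the e-max and exponential figures using the curve parameters of the original calculation; the ranges given here should not become fixed text. Put the same note in protocol 10.1 at the next amendment.
2. **SAP 2.4.** Reword the first outcome as *no effect of NR shown*. Add: *Minimum effective dose means the lowest dose shown superior to placebo in this procedure; it does not imply that lower doses have no effect.*
3. **SAP 6.1.** Report the hazard ratio with 95% CI for all three doses wherever the sequence stops, labelled descriptive after the stop.

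The cost is one note, two wording changes and up to two extra descriptive estimates, with no change to tests, alpha or patient numbers. The price is a less favourable power statement and a more modest dose conclusion. Protocol 10.4 allows changes to the plan until database lock, so the SAP edits should be made before then; afterwards a reworded decision rule would look driven by results. The protocol note needs Ethics Committee approval (protocol 11.4) and can wait.

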2.4 Statistical Framework

The statistical framework will be based on the context of dose-finding, for which there are two main approaches: "regression" and "contrast" (Senn, 2007). In the regression approach, the actual doses used in the trial are viewed as samples from a dose continuum, and the purpose is to estimate the dose response curve. In the contrast approach, interest is on one or (more likely) several contrasts between the doses used in the trial. The former is the most explorative and may be sensitive to modeling choices, small number of doses, and over-fitting, especially for small sample sizes (such as in this trial). The latter is well suited for determining the *minimum effective dose*, in which we compare the different doses to placebo.

Specification of the Primary Objective

The primary objective of this study will be to establish the minimum effective dose of NR on shortening recovery time after critical illness. The primary outcome is length of hospital stay in days (see Section 5.1 for details).

There is only one identified primary analysis in this trial. All other efficacy analyses will be regarded as supportive or exploratory.

Hypothesis Setup

Let μ_1 , μ_2 , μ_3 , and μ_4 denote the mean lengths of hospital stay for placebo, low dose (250 mg/day), medium dose (500 mg/day), and normal dose (1 g/day), respectively.

The statistical scheme to account for multiple testing is based on the *closed multiple test procedure* of Marcus et al. (1976). Under the monotonicity assumption, we define a set of elementary null hypotheses (the many-one comparison) with a preassigned order of performing the tests (Williams, 1971):

Step 1: Test the null hypothesis H_0 : $\mu_1 = \mu_4$ Step 2: Test the null hypothesis H_0 : $\mu_1 = \mu_3$ Step 3: Test the null hypothesis H_0 : $\mu_1 = \mu_2$

The test in Step 1 is carried out with a nominal significance level of α = 0.05. If the test is rejected, the test in Step 2 can be carried out, also with α = 0.05. If the test in Step 2 is rejected, the test in Step 3 can be carried out (with α = 0.05). The tests in steps 2 and 3 are only performed if the preceding null hypothesis is rejected, which – together with the monotonicity assumption – ensures that the significance level is preserved for the entire procedure (Williams, 1971; Bauer, 1991). All tests will be performed two-sided.

Decision Rule

The testing scheme above can result in four situations:

- 1. The null hypothesis in Step 1 is not rejected. Decision: No effect of NR for the doses in the study.
- 2. The null hypothesis in Step 2 is not rejected. Decision: The normal dose is the minimum effective dose.
- 3. The null hypothesis in Step 3 is not rejected. Decision: The medium dose is the minimum effective dose.
- 4. The null hypothesis in Step 3 is rejected. Decision: The low dose is the minimum effective dose.

Assumption

The dose response is assumed to be monotone, i.e., the effect of low dose is less than or equal to the effect of medium dose, which is less than or equal to the effect of normal dose. Or, consequently, that the mean length of hospital stay decreases monotonous from placebo (μ_1) to normal dose (μ_4):

 $\mu_1 \ge \mu_2 \ge \mu_3 \ge \mu_4$.

Adaptation to Estimation

Hypothesis testing will only be performed for the primary outcome. For all secondary outcomes, estimation of treatment effect with 95% (two-sided) confidence intervals will be carried out instead of hypothesis testing in each of the three steps described above. The overall statistical approach will be the same; however, the criterion for performing steps 2 and 3 is that the 95% confidence interval from the preceding step does not contain the null effect value.

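### The minimum-effective-dose rule in SAP 2.4 has no direction condition, so a significantly longer stay on 1 g/day would, as written, end in a declared minimum effective dose

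*SAP*

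**What the plan says.** SAP 2.4 (Hypothesis Setup) states three null hypotheses of equal means, placebo against 1 g/day, then 500 mg/day, then 250 mg/day. "The test in Step 1 is carried out with a nominal significance level of α = 0.05". On continuing: "If the test is rejected, the test in Step 2 can be carried out, also with α = 0.05", and again: "The tests in steps 2 and 3 are only performed if the preceding null hypothesis is rejected". On sidedness: "All tests will be performed two-sided".

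The Decision Rule gives four possible results. The first is: "The null hypothesis in Step 1 is not rejected. Decision: No effect of NR for the doses in the study". The second is: "The null hypothesis in Step 2 is not rejected. Decision: The normal dose is the minimum effective dose". The third follows the same pattern for the medium dose. The last is: "The null hypothesis in Step 3 is rejected. Decision: The low dose is the minimum effective dose". None says which group must have the shorter stay.

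The Assumption paragraph of the same section takes it that "the mean length of hospital stay decreases monotonous from placebo" to the normal dose, written μ1 ≥ μ2 ≥ μ3 ≥ μ4. For secondary outcomes, Steps 2 and 3 open when the preceding 95% confidence interval excludes the null value, again on either side. SAP 3.1 and 6.1 add no direction condition: significance is a two-sided P below 0.05, and the test is of a hazard ratio of 1.

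**The concern.** A rule meant to find a dose that shortens stay should not be satisfied by a dose that lengthens it. Read as written, this one can be. Once Step 1 is rejected, only the second, third and fourth outcomes remain, and each names an effective dose. A rejection caused by longer stays on NR is handled like one caused by shorter stays, and it also opens the lower-dose tests. No outcome covers a significant difference favouring placebo.

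This matters because the rule yields the trial's only confirmatory conclusion: SAP 2.4 identifies one primary analysis and treats all other efficacy analyses as supportive or exploratory.

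**Working it through.** **Inputs.** From SAP 2.3: Weibull stay with scale 18 and shape 2.2; 18 placebo patients and 10, 10 and 20 on 250 mg, 500 mg and 1 g/day; maximal reduction 33%. From SAP 2.4: two-sided tests at 0.05 in fixed order. From SAP 6.1: Weibull regression, hazard ratio (HR) for discharge. The simulations use two-sided Wald tests, a shared placebo group and no censoring.

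**The plan's own figures.** The Weibull quantile is 18 × (−ln(1 − p))^(1/2.2). It gives a median of 15.2 and quartiles of 10.2 and 20.9, matching the stated 15 and 10 to 21. The stated power of about 80% belongs to the MCPMod dose-response test, not to the stepwise rule. The documents give neither its alpha nor its curve parameters. With assumed values (ED50 100 to 500 mg, exponential delta 250 to 500 mg) the recomputed power is 77 to 84% at one-sided 0.025 with shape known, and 72 to 80% with shape estimated. The stated figure is consistent with this.

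**What the rule returns when Step 1 is rejected because stay is longer on 1 g/day:**

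| Step 2 | Step 3 | Matching outcome |
|---|---|---|
| not rejected | not run | normal dose is the minimum effective dose |
| rejected | not rejected | medium dose is the minimum effective dose |
| rejected | rejected | low dose is the minimum effective dose |

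**How often, with no true effect.** Equality of all four means satisfies the monotonicity assumption.
- Nominal: a dose is declared exactly when Step 1 is rejected, so 5% in all; the wrong-direction part is 0.05/2 = 2.5%, or half.
- Step 1 alone, 6,000 simulated trials: significantly shorter 2.8%, significantly longer 3.2%, total 6.0%.
- Whole procedure, 4,000 simulated trials: declarations that began with a longer stay on 1 g/day, 2.35% + 0.525% + 0.225% = 3.1%. Those that began with a shorter stay, 2.575% + 0.575% + 0.15% = 3.3%. Total 6.4%, of which 3.1/6.4 = 48% are in the wrong direction.

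Across simulation runs, about 3 to 4% is a fair summary. The excess over 2.5% appears to be small-sample behaviour of the Wald test, not an effect of the decision rule.

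**How often, if the assumption fails.** Suppose 1 g/day multiplies stay by c. The values of c are assumed; the documents give none, and SAP 2.4 excludes any c above 1. Then HR = c^(−2.2), and the Schoenfeld approximation for 20 against 18 with every patient discharged is Φ(|ln HR| × √(38 × 18/38 × 20/38) − 1.96), where the square root is √9.474 = 3.078.
- c = 1.20: HR = 0.670; 0.401 × 3.078 − 1.96 = −0.725; Φ = 23%. Simulated 24 to 25%.
- c = 1.33: HR = 0.534; 0.627 × 3.078 − 1.96 = −0.029; Φ = 49%. Simulated 49 to 50%.

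With harm rising linearly to c = 1.33 at 1 g/day, the whole procedure names the normal dose in 39% of trials, the medium dose in 9% and the low dose in 3%.

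**With a direction condition.** Under no true effect, the chance of declaring any dose falls from 5% to 2.5% nominally (6.4% to 3.3% simulated). Under c = 1.33 it falls from 50% to about 0%. For a true 33% reduction, Step 1 power is 76% either way, because wrong-direction rejections were 0.0%.

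**The case against.** The strongest reply is that the SAP fixes the direction elsewhere. Its hypotheses are set up under a monotonicity assumption with a sign, so the only alternative to equality is a shorter stay on NR, and a list with no harm branch follows from that. The objective is to shorten recovery, so a dose that lengthens stay is not effective by definition. The outcome list is also shorthand: the second outcome does not even say that Step 1 was rejected. SAP 6.1 requires the HR with its interval, a plot of means and individual values by dose, and Kaplan-Meier curves, so the direction cannot be hidden. Safety is reviewed separately by the monitoring committee.

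Much of this stands, and it limits the weight of the point. Within the SAP's own model the worst case is the nominal 2.5%; any true benefit makes it smaller. But an assumption about true means is not a condition on an observed result, and it permits the no-effect case in which wrong-direction rejections occur. Nor does the SAP say which side of an HR of 1 is favourable: above 1 favours NR for discharge, below 1 favours NR for mortality, and both are to be reported in the main article.

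Three stronger readings are tempting and are not supported:
- A reader might infer that the tests are two-sided in order to allow for harm. The documents give no reason; it may be convention.
- A reader might take the 25% and 50% figures as the trial's expected risk. They require true harm that the SAP assumes away and that no figure in the documents suggests.
- A reader might fear that a benefit at 1 g/day followed by a harmful result at 500 mg/day would move the declared dose down. The wording allows it, but it did not occur in 4,000 simulated trials in any of five scenarios.

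**Conclusion.** The rule is wrong as written: followed literally, a significant result in favour of placebo at Step 1 can only end in a declared minimum effective dose. The defect is modest. With no true effect it arises in a nominal 2.5% of trials (about 3 to 4% simulated) and makes up about half of false dose declarations. The figures of about 25% and 50% are conditional on assumed lengthening of 20% and 33% and on failure of monotonicity. All simulated figures rest on the SAP's Weibull inputs and group sizes, with no censoring. No sample size, estimate or interval changes, and the reported results would show the direction. A reader should not conclude that the plan conceals harm or that its nominal two-sided 5% level is exceeded because of this rule; what needs correcting is the link from rejection to declaration.

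**What to change.** In SAP 2.4, keep two-sided P values but count a step as passed only if P < 0.05 and the estimate favours NR, meaning a shorter stay (HR for discharge above 1). State the condition as shorter stay as well as through the HR, because SAP 6.5 allows a lognormal model if proportional hazards fail.

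Add a fifth outcome: if a step is rejected in favour of placebo, testing stops, that step supports no effective dose, and the longer stay on NR is reported.

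Apply the same direction condition to the confidence-interval criterion for secondary outcomes, naming the favourable side for each one.

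The cost is two sentences for the primary rule and a clause for the secondary outcomes. Power for benefit and sample size do not change. Protocol 10.4 allows changes to the plan until the database is locked, so the correction belongs before that point.
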